2. DATA ANALYSIS CHANGES

2.1 Definition of Baseline for Exploratory Efficacy Endpoints and Safety Endpoints

The SAP version 1.0 defines the baseline value for the primary efficacy endpoint hs-CRP, secondary efficacy endpoint Serum Amyloid A, and exploratory efficacy endpoints Hemoglobin, Serum Albumin, and NT-pro-BNP as the average of lab value at Day 1 and prior assessment(s). For the CARES Corvidia ePRO endpoint, baseline is defined as the average of 7 consecutive measurements (Day -7 to Day -1) prior to first dose initiation.

Similarly, baseline for all exploratory efficacy endpoints will be defined as follows:

- For endpoints where lab assessments were collected at multiple visits prior to the initiation of study drug, baseline will be calculated as average of all values prior to the first dose.
- For endpoints where lab assessments were collected at Day 1 only, baseline will be defined as the Day 1 value.

For all safety endpoints, baseline will be defined as the Day 1 value. If missing, the last evaluation prior to the initiation of the study drug will be considered the baseline.

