2 STUDY OVERVIEW

2.1 Study Objectives

Patients with non-dialysis-dependent chronic kidney disease (NDD-CKD), who have evidence of systemic inflammation with increased cardiovascular risk, will be enrolled into this trial. The purpose of this trial is to determine a dose to select for a potential cardiovascular outcome trial with Ziltivekimab.

2.1.1 *Primary Objective*

The primary objective is to evaluate the effects of Ziltivekimab compared to placebo on a marker of inflammation: high-sensitivity C-reactive protein (hs-CRP).

2.1.2 *Secondary Objectives*

The secondary objectives of the study are as follows:

- To evaluate the effects of Ziltivekimab compared to placebo on a markers of inflammation and cardiovascular risk: serum amyloid A (SAA) and fibrinogen.

2.1.3 *Safety Objectives*

- To evaluate the safety of three dose levels of Ziltivekimab compared to placebo.

2.1.4 *Pharmacokinetic Objectives*

- To evaluate the pharmacokinetics (PK) and PK-pharmacodynamic (PK-PD) modeling of Ziltivekimab following multiple doses at three different dose levels.

2.1.5 *Exploratory Objectives*

The exploratory objectives of the study are as follows:

- To evaluate the effects of Ziltivekimab compared to placebo on markers of anemia (hemoglobin).
- To evaluate the effects of Ziltivekimab compared to placebo on markers of inflammation-malnutrition (albumin).
- To evaluate the effects of Ziltivekimab compared to placebo on markers of cardiovascular risk (i.e. N-terminal prohormone-B-type natriuretic peptide [NT-pro-BNP]).
- To evaluate the effects of Ziltivekimab compared to placebo on additional markers of cardiovascular risk (Suppression of Tumorigenicity 2 [ST2]).

- To evaluate the effects of Ziltivekimab compared to placebo on markers of atherosclerosis risk: LDL-C, triglycerides, ApoB, ApoA1, ApoB/ApoA1, Nuclear Magnetic Resonance (NMR) lipoprotein profile, and Lp (a).
- To evaluate the effects of Ziltivekimab compared to placebo on markers of kidney function: cystatin C, estimated Glomerular Filtration Rate (eGFR) and kidney damage: urine albumin-to-creatinine ratio (UACR).
- To determine Ziltivekimab trough drug levels following multiple Ziltivekimab doses at three different dose levels.

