2.3.5 Safety Endpoints

- Proportion of patients with AEs, serious AEs (SAEs), severe hematologic AEs, severe non-hematologic AEs, and AEs leading to discontinuation.
- Proportion of subjects with thrombolysis in myocardial infarction (TIMI) major bleeding event.
- Description and frequency of events of special interest by
 - Serious infections.
 - Severe injection-related reactions.
 - Gastrointestinal perforations.
 - Hypersensitivity reaction during study drug administration.
 - Anaphylaxis occurring at any time, even if considered unrelated to the study drug.
 - Neutrophil < 500/mm³ (severe) or neutrophil < 1000/mm³ (severe) with evidence of concurrent infection. These events will be separately summarized by treatment group and dose.
 - Thrombocytopenia (platelet count < 50,000/mm³ [severe]) or platelet count < 75,000/mm³ (moderate) with evidence of concurrent TIMI major bleeding. These events will be separately summarized by treatment group and dose.
 - Malignancies
- Description of additional safety assessments by treatment group and dose: vital signs, ECG, clinical laboratory, and anti-drug antibodies (binding and neutralizing).

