The immunogenic potential of Ziltivekimab will be assessed by summarizing the number and percentage of patients who develop detectable anti-drug antibodies (ADA). Anti-drug antibody titers will be summarized descriptively for ADA positive samples and the impact of ADA on PK will be assessed if data allows.

3.7.7 *Bleeding Events*

Bleeding events will be classified using the Thrombolysis In Myocardial Infarction (TIMI) Bleeding Classification

Table 4 TIMI Bleeding Classification

Parameter	Criteria
Major	Intracranial hemorrhage or a ≥ 5 g/dL decrease in the hemoglobin concentration or a $\geq 15\%$ absolute decrease in the hematocrit

Minor	Observed blood loss: ≥ 3 g/dL decrease in the hemoglobin concentration or $\geq 10\%$ decrease in the hematocrit. No observed blood loss: ≥ 4 g/dL decrease in the hemoglobin concentration or $\geq 12\%$ decrease in the hematocrit
Minimal	Any clinically overt sign of hemorrhage (including imaging) that is associated with a <3 g/dL decrease in the hemoglobin concentration or $<9\%$ decrease in the hematocrit
All TIMI definitions take into account blood transfusions, so that hemoglobin and hematocrit values are adjusted by 1 g/dL or 3%, respectively, for each unit of blood transfused. Therefore, the true change in hemoglobin or hematocrit if there has been an intervening transfusion between two blood measurements is calculated as follows: Δ Hemoglobin = [baseline Hgb – post-transfusion Hgb] + [number of transfused units]; Δ Hematocrit = [baseline Hct – post-transfusion Hct] + [number of transfused units \times 3].	

Tables will be generated for each of the TIMI Bleeding Classification parameters by treatment and in total. Bleeding events will also be listed.

3.7.8 Exploratory Analyses of Efficacy and Safety Endpoints Based on Baseline Hemoglobin (≥ 11 or <11 g/dL)

Exploratory analyses may be performed for the primary and secondary efficacy endpoints with a stratified analysis by baseline hemoglobin (≥ 11 g/dL or <11 g/dL) and CKD stage (3, 4 or 5).

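### TIMI bleeding grades have no named reference haemoglobin other than a pre-dose baseline, so haemoglobin drift before a bleed shifts the cut-offs, and the Minor and Minimal haematocrit criteria omit that the fall is absolute

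*SAP*

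**What the plan says.** Clinical SAP section 3.7.7 (Bleeding Events), Table 4, sets the grades:

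- **Major:** intracranial haemorrhage, a fall of at least "5 g/dL decrease in the hemoglobin concentration", or a 15% "absolute decrease in the hematocrit".
- **Minor:** with observed blood loss, a fall of at least 3 g/dL or 10% in haematocrit. Under "No observed blood loss", at least 4 g/dL or 12%.
- **Minimal:** overt bleeding with a fall below 3 g/dL or below 9% in haematocrit.

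No row says what the fall is measured from. A note adjusts for transfusion at 1 g/dL or 3% per unit. It applies "if there has been an intervening transfusion between two blood measurements", and gives the haemoglobin change as "baseline Hgb – post-transfusion Hgb] + [number of transfused units", with the same form for haematocrit at 3 per unit.

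Baseline is defined in three places that do not agree:

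- Addendum section 2.1: "For all safety endpoints, baseline will be defined as the Day 1 value", or the last pre-drug value if Day 1 is missing.
- Addendum section 3: the addendum's changes were applied only to laboratory and PRO endpoints that are exploratory efficacy endpoints.
- Clinical SAP section 3.1.3: haemoglobin baseline averages values before randomization and Day 1. Haematocrit is not named there and falls under the general rule, the latest value before study drug.

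Section 2.3.5 lists as a safety endpoint "Proportion of subjects with thrombolysis in myocardial infarction (TIMI) major bleeding event". TIMI major bleeding also forms part of the thrombocytopenia event of special interest in that section.

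**The concern.** A TIMI grade is meant to reflect the blood lost in the event. The transfusion note starts from that idea, since it speaks of two measurements with a transfusion between them, but then writes the first of them as baseline. Under every definition available to the programmer, baseline is pre-dose. The last follow-up visit window is Days 218 to 224, so the reference can be (218 − 1)/7 = 31 weeks old or slightly more.

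Haemoglobin is not fixed over that time, and section 2.1.5 makes it an object of study: "To evaluate the effects of Ziltivekimab compared to placebo on markers of anemia (hemoglobin". The grade would then mix the bleed with whatever happened to haemoglobin beforehand. If haemoglobin change differed between arms, so would the grading error.

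The haematocrit wording is a second, smaller defect. With absolute stated only in the Major row, a programmer could read the Minor and Minimal percentages as relative falls.

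**Working it through.** **The table's own scale.** The plan gives no bleeding rate and no haemoglobin effect, so there is no such figure to reproduce. Table 4 does contain one internal equivalence: one unit counts as 1 g/dL or 3 haematocrit points. Applied to the haemoglobin cut-offs:

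- Major: 5 × 3 = 15 points; the table says 15%.
- Minor, no observed loss: 4 × 3 = 12; the table says 12%.
- Minimal limit: 3 × 3 = 9; the table says 9%.
- Minor, observed loss: 3 × 3 = 9; the table says 10%, close to it.

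The rows therefore fit in absolute points. As relative falls from an assumed haematocrit of 33%, they do not:

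- 10% is 3.3 points, or 3.3/3 = 1.1 g/dL, beside 3 g/dL in the same criterion.
- 12% is 3.96 points, or about 1.3 g/dL, beside 4 g/dL.
- 9% is 2.97 points, or about 1.0 g/dL, beside 3 g/dL.

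**The reference value.** Let B be pre-dose haemoglobin, r the change from B to just before the bleed, L the true loss and u the units transfused, each adding 1 g/dL as in the table.

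- Post-transfusion haemoglobin = B + r − L + u.
- Computed fall = B − (B + r − L + u) + u = **L − r**.

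The units cancel. With u = 0 the result is the same if a pre-dose baseline is also used for bleeds without transfusion. With the last pre-bleed value (B + r) as reference, the computed fall is L.

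Example: B = 10.5, r = +1.0, L = 5.5, u = 2. Post-transfusion haemoglobin is 10.5 + 1.0 − 5.5 + 2 = 8.0. The formula gives 10.5 − 8.0 + 2 = 4.5, Minor. From the pre-bleed value, 11.5 − 8.0 + 2 = 5.5, Major.

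True loss needed for each grade (g/dL; the values of r are assumptions):

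| r | Major | Minor, no observed loss | Minor, observed loss |
|---|---|---|---|
| −1.0 | 4.0 | 3.0 | 2.0 |
| −0.5 | 4.5 | 3.5 | 2.5 |
| 0 | 5.0 | 4.0 | 3.0 |
| +0.5 | 5.5 | 4.5 | 3.5 |
| +1.0 | 6.0 | 5.0 | 4.0 |
| +1.5 | 6.5 | 5.5 | 4.5 |
| +2.0 | 7.0 | 6.0 | 5.0 |

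Only losses within r of a cut-off change grade. With observed bleeding and r = +1.0, losses of 5.0 and 5.5 drop from Major to Minor, and losses of 3.0 and 3.5 drop from Minor to Minimal; losses of 4.0, 4.5 and 6.0 or more keep their grade. With r = −1.0, losses of 4.0 and 4.5 rise from Minor to Major.

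**Conditional illustration.** Assume every bleed in a group follows the same drift r, and that acute falls are log-normal with (median, log-SD) of (2.0, 0.6), (2.5, 0.6) or (3.0, 0.5). The number graded Major by haemoglobin, relative to the number truly at or above 5 g/dL, is P(L ≥ 5 + r)/P(L ≥ 5). For median 2.0 and r = +1.0 it is 0.0335/0.0634 = 0.53. Over the three settings:

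- r = +0.5: 0.72 to 0.76
- r = +1.0: 0.53 to 0.58
- r = +1.5: 0.39 to 0.45
- r = −0.5: 1.32 to 1.39
- r = −1.0: 1.75 to 1.96

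These ratios use the haemoglobin criterion alone and no event rate. The documents give neither the distribution of falls nor r.

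**The case against.** The formula is written only for bleeds with an intervening transfusion, and there baseline could be read as the earlier of the two measurements. The first part stands: for other bleeds the reference is unspecified, not fixed at Day 1. That is itself a gap, and the only definitions a programmer can turn to are pre-dose.

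The Day 1 rule is not clean either, given addendum section 3 and the averaged haemoglobin baseline in section 3.1.3. This also stands, but it changes only which pre-dose value is used.

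A reader might infer that the rule hides bleeds in the active arms only, or favours active drug. The documents do not support that. Haemoglobin is an exploratory question with no stated size or direction of effect. The offset follows each patient's own drift in whichever arm, it runs both ways, and intracranial haemorrhage is Major regardless. Nor does every rise lower a grade.

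A reader might also infer that a relative haematocrit reading would turn ordinary laboratory variation into Minor bleeds in patients who never bled. Section 3.7.7 classifies bleeding events; it prescribes no laboratory screen of other patients. The one listed endpoint, Major, does say absolute.

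The practical effect is limited. No test of bleeding is specified, with about 60 patients per arm few Major events may occur, and bleeding events and all laboratory values will be listed.

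Finally, the last value before recorded onset may already be lowered in a slow or occult bleed, which would understate the loss. That is a genuine drawback of the remedy.

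**Conclusion.** The point holds as a gap in definition. If the pre-dose baseline is used, as the text leads a programmer to do, the computed fall is the true loss minus any earlier rise, and the cut-offs become 5+r, 4+r and 3+r. That is algebra and needs only the table's own allowance of 1 g/dL per unit. How many events change grade depends on r and on the distribution of losses, neither of which the documents give, so the ratios above are illustrations only. The error is differential only if haemoglobin change differs by arm, which the trial examines but does not assert. The haematocrit wording is a lesser point that the table's own arithmetic settles in favour of absolute points. The change should be made because a named safety endpoint depends on it; it does not touch the primary analysis.

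**What to change.** - In clinical SAP section 3.7.7, define the reference for TIMI grading, with or without transfusion, as the last haemoglobin and haematocrit before onset of the bleeding event. Use the pre-dose baseline only if no later pre-event value exists.
- Exempt this endpoint from the Day 1 rule in addendum section 2.1, and reconcile addendum sections 2.1 and 3 with clinical SAP sections 3.1.3 and 3.7.7.
- Report the grade from the pre-dose baseline as a sensitivity listing, so that a slow bleed already under way at the last pre-onset value can be seen.
- Write absolute in the haematocrit criteria of the Minor and Minimal rows.

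The cost is a few sentences and a small programming change. Haematology is already scheduled at the clinic visits, so no further data are needed.

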4 ANALYSIS TIMING

4.1 Blinding and Database Lock

All investigators and patients will remain blinded throughout the study. Additionally, members of the study team including operations team, data management, and statistical team will also remain blinded until the final database lock.

Once all subjects complete Visit 7 (Week 13), the database will be cleaned and locked for the purpose of analyzing the efficacy and safety data for primary analysis. An independent, unblinded statistician will perform this analysis and provide results to a team at Corvidia that will use this information to plan future studies. No subject-level data will be provided to Corvidia or any members of the project team so that the treatment assignments of all subjects remains blinded until completion of the entire study. A formal Blinding Plan will be approved for implementation in the study, prior to the Visit 7 (Week 13) lock and statistical analysis.

After the last subject completes the last visit, the final database will be cleaned, locked and analysis will be performed. At this time, members of the study team will become unblinded to the subject treatment assignments.

Prior to the each database lock, the blinded team may perform a blinded data review using tables, figures, and listings.

4.2 Interim Analysis

Interim analysis will not be performed for this study,

4.3 Pre-Final Analysis

After the final database is locked and exclusions from analysis populations have been finalized, the randomized treatment assignments will be unblinded and the pre-final analysis will be generated. Pre-final TFLs will be provided approximately 4 weeks after final database lock.

4.4 Final Analysis

After all comments on the pre-final analysis have been resolved and the study database is declared final, the final analysis will be generated. Final TFLs will be provided approximately 1 week after the study database is declared final. If there were no changes to the pre-final analysis or the study database, the pre-final TFLs may be considered final. In addition to TFLs, Study Data Tabulation Model (SDTM) data and Analysis Data Model (ADaM) data along with associated files will be provided. Associated files may include: annotated CRFs, SDTM specifications, SDTM programs, ADaM specifications, ADaM programs, TFL programs, and Clinical Data Interchange Standards Consortium (CDISC) Define packages for both SDTM and ADaM data.

5 CHANGES FROM PROTOCOL-SPECIFIED STATISTICAL ANALYSES

The schedule of procedures defined in the protocol is listed as Table 1 in this SAP. The schedule of procedures states that cardiac risk markers (SAA, fibrinogen, and ST2) will be assessed at Visit Weeks 1, 13, and 23/ET respectively. The SAP clarifies that SAA will be analyzed for percentage change from baseline where the baseline for SAA will be evaluated as the average of values at Visit Week -1 and Day 1, and the End of Treatment will be evaluated as the average of values at Visit Week 23 and Week 24/ET.

Due to the impact of the Coronavirus Disease 2019 (COVID19) pandemic on the RESCUE clinical trial, an immediate discontinuation of dosing was announced on March 18, 2020 to ensure the safety of trial patients. The announcement required the early termination visit to be scheduled as early as possible for ongoing patients followed by their entry into the safety follow-up period.

At the time of discontinuation of the study, approximately 140 patients had completed the 24-week treatment period and more than 120 patients were non-completers of the treatment period. As a result, the methods for primary, secondary, or exploratory endpoints that required analysis of change or percent change from baseline to end of treatment were reconsidered as follows:

- For patients who were early terminated from the RESCUE trial due to COVID19 and had completed Week 13 efficacy assessments, the End of Treatment visit will be derived as the average of their last 2 visits after Week 13 including Week 13. The End of Treatment value for such patients will be defined as the average of assessments at Week 13 and Week 17 or Week 17 and Week 21, or Week 21 and Week 23 depending upon the last two completed visits for each patient. The rationale behind taking the average of the last 2 visits as End of Treatment visit is that Ziltivekimab remains effective in the same manner after three months of dosing which is equivalent to the Week 13 endpoint.

MMRM analysis performed for baseline to End of Treatment is based on (1) the assumption of missing at random with small amount of missing data and (2) End of Treatment (the average of Week 23 and Week 24) with the same time window for all patients. Given (1) the missing data

for a large number of early terminated patients due to COVID19 and (2) the time window for End of Treatment visit (the average of the last 2 visits including and after Week 13) varying from patient to patient, MMRM results may not be appropriate to analyze change or percentage change from baseline to End of Treatment. Therefore, analysis for change or percentage change from baseline to End of Treatment will be performed using an analysis of covariance model (ANCOVA), where the percent change or change from baseline to End of Treatment described above will be used as the outcome variable. The ANCOVA model will also include baseline hemoglobin (≥ 11 or < 11 mg/dL), CKD Stage (3, 4 or 5), and treatment group as factors; baseline hs-CRP and the baseline value (for efficacy parameters other than hs-CRP) as covariates.

The sample SAS code for ANCOVA analysis is provided below:

```
*****
*Note: PCHG = Percent change from baseline for efficacy parameter
*      HGB = Baseline Hemoglobin category ( $\geq 11$  or  $< 11$  mg/dL)
*      CKD = CKD Stage (3, or 4/5)
*      TRT = Treatment group
*      CRP = Baseline hs-CRP value
*      BASE = Baseline value for efficacy parameter
*****;

proc mixed data=efficacy ;
  class HGB CKD TRT;
  model pchg=HGB CKD TRT BASE CRP;
  lsmeans TRT/ pdiff=control('0') cl ;
  ods output diffs=Diff;
run;
```

Analysis of change or percent change from baseline to Week 13 for the primary, secondary, and exploratory endpoints will be carried out using MMRM analysis as originally planned and will include scheduled post-baseline visits up to and including Week 13. Details of MMRM analysis can be found in section 3.4.1 of this SAP.

6 PROGRAMMING SPECIFICATIONS

Analyses will be performed using SAS® version 9.3 or higher. All available data will be presented in subject data listings which will be sorted by subject and visit date as applicable. Detailed Programming Specifications will be provided in a separate document.

